**LIST OF ABBREVIATIONS**

ADA	Anti-drug Antibody
AE	Adverse Event
ALT	Alanine Aminotransferase
ANCOVA	Analysis of Covariance
ANOVA	Analysis of Variance
AP	Alkaline Phosphatase
AST	Aspartate Aminotransferase
ATC	Anatomical Therapeutic Classification
AUC	Area Under the Concentration-Time Curve
AUC (0-inf)	Area Under the Concentration-Time Curve Extrapolated to Infinity
AUC (0-last)	Area Under the Concentration-Time Curve from Time of Dosing to Time of Last Measurable Concentration
BMI	Body Mass Index
BP	Blood Pressure
BQL	Below the Quantification Limit
BUN	Blood Urea Nitrogen
C	Celsius
CAR	Clinical Agent Repository
CHEM	Chemistry
CHIKV	Chikungunya Virus
CI	Confidence Interval
CL	Clearance
cm	Centimeter
C max	Maximum Concentration
COAG	Coagulation
CRF	Case Report Form
CS	Clinically Significant
CSR	Clinical Study Report
CV	Coefficient of Variation
DBP	Diastolic Blood Pressure
DHHS	Department of Health and Human Services
DMID	Division of Microbiology and Infectious Diseases

**List of Abbreviations (continued)**

ECG	Electrocardiogram
eCRF	Electronic Case Report Form
eGFR	Estimated Glomerular Filtration Rate
ET	Early Termination
FDA	Food and Drug Administration
GM	Geometric Mean
GMT	Geometric Mean Titer
GMFR	Geometric Mean Fold Rise
HCT	Hematocrit
HEM	Hematology
HGB	Hemoglobin
HLGT	High Level Group Term
ICH	International Conference on Harmonisation
IND	Investigational New Drug
IV	Intravenous
IRB	Institutional Review Board
kg	Kilogram
L	Liter
LLN	Lower Limit of Normal
LLOQ	Lower Limit of Quantification
m	Meter
mAb	Monoclonal Antibody
MedDRA	Medical Dictionary for Regulatory Activities
$\mu\text{g}$	Microgram
mg	Milligram
mL	Milliliter
MM	Medical Monitor
MRSD	Maximum Recommended Starting Dose
N	Number
NCA	Noncompartmental Analysis
NCS	Not Clinically Significant
NHP	Non-human primate

**List of Abbreviations (continued)**

NIAID	National Institutes of Allergy and Infectious Diseases
NIH	National Institutes of Health
NOAEL	No Observed Adverse Effect Level
NSAID	Non-steroidal Anti-inflammatory Drug
ONR	Outside Normal Range
OTC	Over-the-counter
PBPK	Physiological Based Pharmacokinetic
PI	Principal Investigator
PK	Pharmacokinetics
PT	Preferred Term
QNS	Quantity Not Sufficient
QTcF	QT interval corrected for heart rate by Fridericia's cube root correction
RBC	Red Blood Cell
RCD	Reverse Cumulative Distribution
SAE	Serious Adverse Event
SAP	Statistical Analysis Plan
SBP	Systolic Blood Pressure
SD	Standard Deviation
SDCC	Statistical and Data Coordinating Center
SMC	Safety Monitoring Committee
SOC	System Organ Class
SRC	Safety Review Committee
SUSAR	Serious and Unexpected Suspected Adverse Reaction
SWFI	Sterile Water for Injection
$t_{1/2}$	Apparent terminal elimination half-life
TEAE	Treatment-emergent Adverse Event
$T_{max}$	Time of Maximum Concentration
UA	Urinalysis
ULN	Upper Limit of Normal
UP	Unanticipated Problem
$V_d$	Volume of Distribution
VS	Vital Signs

**List of Abbreviations (continued)**

WBC	White Blood Cells
WHO	World Health Organization
$\lambda_z$	Elimination Rate Constant

## 1. PREFACE

The Statistical Analysis Plan (SAP) for “A Phase 1, Randomized, Double-Blind, Multi-Site, Single Dose Escalation Study to Evaluate the Safety, Pharmacokinetics, and Immunogenicity of SAR440894 vs Placebo in Healthy Adults” (Division of Microbiology and Infectious Diseases (DMID) Protocol 18-0006) describes and expands upon the statistical information presented in the protocol.

This document describes all planned analyses and provides reasons and justifications for these analyses. It also includes sample tables, listings, and figures planned for the final analyses. Regarding the final analyses and Clinical Study Report (CSR), this SAP follows the International Conference on Harmonisation of Technical Requirements for Registration of Pharmaceuticals for Human Use (ICH) Guidelines, as indicated in Topic E3 (Structure and Content of Clinical Study Reports) [1], and more generally is consistent with Topic E8 (General Considerations for Clinical Trials) [2] and Topic E9 (Statistical Principles for Clinical Trials) [3]. The structure and content of the SAP provides sufficient detail to meet the requirements identified by the FDA and ICH, while all work planned and reported for this SAP will follow internationally accepted guidelines published by the American Statistical Association [4] and the Royal Statistical Society for statistical practice [5].

This document contains four sections: (1) a review of the study design, (2) general statistical considerations, (3) comprehensive statistical analysis methods for safety, pharmacokinetics (PK), and immunogenicity outcomes, and (4) a list of proposed tables, figures, and listings. Within the table, figure, and listing mock-ups (Appendices 1, 2, and 3), references to CSR sections are included. Any deviation from this SAP will be described and justified in protocol amendments and/or in the CSR, as appropriate. The reader of this SAP is encouraged to also review the study protocol for details on conduct of the study and the operational aspects of clinical assessments.

## 2. INTRODUCTION

This is a Phase 1, randomized, double-blind, placebo-controlled, multi-site, single dose escalation study to evaluate the safety, PK, and immunogenicity of intravenous (IV) SAR440894 in healthy adult participants. Five cohorts of 8 participants each will be enrolled in the study. In each of the 5 cohorts, 6 participants will be randomized to SAR440894, and 2 participants will be randomized to placebo. Each cohort will complete the study approximately 22 weeks (150 days) from randomization through Follow-up, which accounts for the long half-life of SAR440894 and will allow for appropriate characterization of the safety, PK, and immunogenicity of SAR440894.

### 2.1. Purpose of the Analyses

This SAP describes the safety, PK, and immunogenicity analyses of 0.3 mg/kg, 1 mg/kg, 3 mg/kg, 10 mg/kg, and 20 mg/kg of SAR440894 that will be included in the CSR. The analyses of safety, PK, and immunogenicity endpoints will be presented in the CSR after completion of the study.

### **3. STUDY OBJECTIVES AND ENDPOINTS**

#### **3.1. Study Objectives**

##### **3.1.1. Primary**

- To determine the safety of single ascending IV infusions of SAR440894 when administered in healthy adults.

##### **3.1.2. Secondary**

- To determine the PK of single ascending doses of 60-minute IV infusions of SAR440894 in healthy adults.
- To assess the immunogenicity of single ascending doses of 60-minute IV infusions of SAR440894 in healthy adults.

#### **3.2. Endpoints**

##### **3.2.1. Primary**

- Occurrence of adverse events (AEs) and serious adverse events (SAEs) following the start of study product administration through the final visit (Day 150 [ $\pm 7$ ]), or Early Termination (ET).
- The occurrence of clinically significant (CS) changes from baseline in vital signs and clinical safety laboratory values following administration of study product through final visit (Day 150 [ $\pm 7$ ]), or ET.
- The occurrence of CS changes in electrocardiogram (ECG) parameters post administration of study product through the final visit (Day 150 [ $\pm 7$ ]), or ET.

##### **3.2.2. Secondary**

- SAR440894 PK after single ascending doses determined from plasma concentrations pre-dose and from the start of infusion until Day 150 ( $\pm 7$ ), or ET.
- SAR440894 immunogenicity determined from presence/absence of plasma human anti-drug antibody (ADA) and measurement of concentration from prior to infusion and at selected time points after infusion up to Day 150 ( $\pm 7$ ) or ET.

#### **3.3. Study Definitions and Derived Variables**

##### **Baseline**

The baseline value will be the last value obtained prior to start of infusion of study product. In the case of ECG assessments, if triplicate measurements were performed at the last visit prior to study product administration, then baseline will be the mean value of the measurements from that visit. For example, if triplicate ECGs are performed on Day 1 prior to dosing, the baseline ECG value for the purpose of analysis would be the mean value of these measurements.

## Treatment Group

Participants will be enrolled and dosed in five dose-ascending cohorts, in which 2 participants will be randomized to placebo and 6 participants will be randomized to SAR440894. The ascending doses of SAR440894 will be 0.3 mg/kg, 1 mg/kg, 3 mg/kg, 10 mg/kg, and 20 mg/kg. Safety, PK, and immunogenicity results will be presented by treatment group. All participants assigned to placebo will be presented as pooled together for the purposes of these analyses. Treatment groups will be presented in the following order: SAR440894 0.3 mg/kg, SAR440894 1 mg/kg, SAR440894 3 mg/kg, SAR440894 10 mg/kg, SAR440894 20 mg/kg, and Placebo. Results from participants assigned placebo will not appear in the PK analyses.

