### 10.2 Sample Size Considerations

No formal sample-size calculations based on testing a statistical hypothesis were performed. This study plans to randomize 40 subjects. The number of subjects was selected to allow sufficient evaluation of safety, and PK of the various single dose regimens to be administered in this study and is consistent with standards of practice for Phase 1 studies.

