### **10.5.1 Safety Analysis Plan**

Safety will be evaluated by presenting summaries of AEs, clinical laboratory evaluations (hematology evaluation, coagulation, chemistry panel, and urinalysis), vital signs, physical exam, and ECGs. Safety variables will be tabulated by dose group and presented for all subjects in the safety population. The safety population will include all subjects who receive any study product and will be grouped by treatment received.

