### **10.5.2 Pharmacokinetic Analysis Plan**

Details of the PK analysis plan will be included in the SAP. Blood samples from all subjects who received a complete dose of SAR440894 (the PK population) will be analyzed for the concentration of SAR440894 by a validated enzyme-linked immunosorbent assay methodology. Plasma concentration-time curves will be constructed for each subject and each dose group. An optional review of SAR440894 time-concentration trends may be performed following each cohort. For each plasma profile, PK parameters including, but not limited to, half-life,  $C_{max}$ , minimum observed plasma concentration ( $C_{min}$ ), time of the maximum observed plasma concentration ( $T_{max}$ ), AUC, clearance, and volume of distribution will be estimated by noncompartmental analysis methods using Version 8.0 or higher of Phoenix WinNonlin®.

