## 4. INVESTIGATIONAL PLAN

### 4.1. Overall Study Design and Plan

This is a Phase 1, randomized, double-blind, placebo-controlled, multi-site, single dose escalation study to evaluate the safety, PK, and immunogenicity of 5 dose levels of IV SAR440894 vs placebo in healthy adults. An overall schematic of the study design is given in [Figure 1](#). The study is expected to enroll approximately 40 participants into 5 cohorts of 8 participants each.

Study enrollment will proceed from Cohort 1 to Cohort 5 starting with the lowest dose and escalating to the next higher dose. In each of the 5 cohorts, participants will be randomized to either SAR440894 (n=6) or placebo (n=2) in an overall 3:1 ratio ([Table 1](#)). In each cohort, 2 sentinel participants will first be randomized to receive SAR440894 or placebo in a 1:1 ratio. The enrolling site principal investigator(s) (PI(s)) will review safety data through Day 4 to confirm no halting criteria are met. After confirmation that sentinel participant halting rules have not been met, the remaining 6 participants in each cohort will be randomized in a 5:1 ratio to SAR440894 and placebo and dosed in pairs of two at least 24 hours apart. Dosing start times will be staggered by at least 15 minutes between participants. Participants will remain in confinement for at least 72 hours after receiving study product. Thereafter, follow-up in each cohort will occur until Day 150 ( $\pm 7$  days) to account for the long half-life of SAR440894 and allow for appropriate characterization of the PK, safety, and immunogenicity of SAR440894.

Blood (plasma) samples will be collected for measuring SAR440894 concentrations for PK analysis at baseline pre-infusion and for 72 hours following the end of infusion. Additional plasma samples will be collected on Day  $7 \pm 1$ , Day  $14 \pm 2$ , Day  $28 \pm 4$ , Day  $56 \pm 4$ , Day  $84 \pm 7$ , Day  $112 \pm 7$ , Day  $150 \pm 7$ , and ET (if needed). Blood (plasma) samples for ADA measurements will be collected for assessing the immunogenicity of SAR440894 at baseline pre-infusion and on Day  $56 \pm 4$ , Day  $112 \pm 7$ , Day  $150 \pm 7$ , and ET. PK and immunogenicity plasma samples will be analyzed by Aptuit (Verona) Srl.

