### **6.3.2. Pharmacokinetics Population**

The PK Population will include all participants who received a complete dose of SAR440894 and have at least one quantifiable post-dose plasma drug concentration record.

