Conduct of non-protocol procedure with increased risk	Safety	
 
- Performing a procedure that put the participant at increased risk of harm (e.g. blood collection over the institutional safety limits, blood collection on a day not required by protocol resulting in an additional stick).
 

Regulatory		
Other	Administrative/regulatory	
 
- Lapse in IRB/EC approval.
 
- Lapse of approval by regulatory agency.
 

Safety		
AE/SAE/UP or other safety event not reported per protocol	Safety	
 
- SAE/UP not reported per protocol to Sponsor, IRB and/or entered into the eCRF according to the protocol/MOP.
 
- Unreported safety event related to halting not entered in eCRFs in the timelines per the MOP or protocol.
 

Required procedure not conducted	Safety	
 
- Failure to perform a required clinical lab test, procedure, or assessment that may affect subject safety because a safety parameter was not collected therefore cannot be assessed.
 

Safety lab not collected	Safety	
 
- Failure to complete and/or review the results of any discharge assessments per protocol prior to discharge (i.e., vital signs check,
 

Other specimen not collected	Safety	

Protocol Deviation	Deviation Category	Example Deviations
		clinical lab assessment, or negative results needed prior to release of quarantine).
Study Product		
Study product temperature excursion	Product storage	- Storage conditions depart from requirements per protocol/IB, and may have compromised product stability. (Excursion not identified/reported to the Sponsor by site prior to site monitor identification).
Improper study agent accountability	Product storage	- Missing or unaccounted study product.
Incorrect dosing/study product administration	Product administration	- Incorrect treatment assignment. - Incorrect study product dispensed/ administered. - Incorrect dose dispensed/administered. - Study product administered to incorrect participant.
Delayed study product administration	Product administration	- Study product was administered out of protocol defined window for administration.
Study product inappropriately unblinded	Blinding policy/procedure	- Participant/study unblinded without adhering to the protocol or MOP unblinding procedures.

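### The SAP builds the pooled placebo group from treatment assigned, while the protocol uses treatment received, and the change is not declared

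*SAP*

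**What the plan says.** **Protocol.** Section 10.5 combines, across cohorts, the subjects who receive placebo into one group. Section 10.5.1 says that the safety population "will include all subjects who receive any study product and will be grouped by treatment received". Both rules follow the product actually given.

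**SAP.** Section 3.3, under Treatment Group, says that safety, PK and immunogenicity results are shown by treatment group, and then: "All participants assigned to placebo will be presented as pooled together for the purposes of these analyses". It adds: "Results from participants assigned placebo will not appear in the PK analyses". Section 6.3.1 admits to the Safety Population anyone given any amount of study product, but does not say how members are grouped. Section 6.3.2 returns to receipt: "The PK Population will include all participants who received a complete dose of SAR440894", provided that at least one post-dose concentration is quantifiable. Section 15 lists two departures from the protocol (creatinine clearance, and which laboratory findings count as AEs). The grouping rule is not among them.

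**Dosing errors.** SAP Appendix 4 foresees them. Its examples of major deviations include "Incorrect study product dispensed/ administered", as well as a wrong assignment, a wrong dose and a wrong recipient.

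**The concern.** The two rules give the same tables unless someone receives a product other than the one assigned. In that case they disagree, and the SAP is the document that will be programmed.

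Under SAP 3.3, a placebo-assigned participant who received SAR440894 stays in the placebo column. Any resulting AE, laboratory change or ADA response is counted in the comparator and is missing from the dose group. This holds even when the error is known and recorded as a deviation, so it does not depend on whether errors are detected. In a first-in-human trial whose primary objective is safety, it moves a possible drug effect to the wrong side of the comparison.

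The SAP also gives the programmer instructions that cannot all be followed. The same participant, after a complete active dose with a quantifiable concentration, belongs to the PK Population (6.3.2) but is kept out of the PK analyses (3.3). With sufficient PK data and a valid post-infusion ADA sample, that participant also enters the PK–Immunogenicity Subset (6.3.4). The ADA-clearance model in 11.1 has five dose groups and no placebo level, so the group given by 3.3 has no place in it.

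**Working it through.** **Planned numbers.** The protocol says: "This study plans to randomize 40 subjects". The SAP gives the split: "In each of the 5 cohorts, participants will be randomized to either SAR440894 (n=6) or placebo (n=2) in an overall 3:1 ratio".

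- Total: 5 × (6 + 2) = 40, which reproduces the stated figure.
- Active: 5 × 6 = 30. Pooled placebo: 5 × 2 = 10.
- Within a cohort: sentinels 1 + 1, then 5 + 1, giving 6 active and 2 placebo.

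One participant is therefore 1/10 = 10.0% of pooled placebo and 1/6 = 16.7% of a dose group.

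**The rules side by side, for a placebo-assigned participant given a complete active dose**

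| Text | Basis | Where the participant goes |
|---|---|---|
| Protocol 10.5 and 10.5.1 | received | dose group |
| SAP 3.3, pooling sentence | assigned | placebo |
| SAP 6.3.1 | membership by receipt, no grouping rule | in the Safety Population, group not stated |
| SAP 6.3.2 | received | PK Population, if a concentration is quantifiable |
| SAP 3.3, PK sentence | assigned | out of the PK analyses |

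**Illustration.** The documents give no dosing-error rate, so the error is assumed: one placebo-assigned participant receives that cohort's active dose and has the only event in the two groups. Intervals are exact Clopper-Pearson, the method named in SAP 6.1. The lower limit is the 2.5% point of Beta(x, n − x + 1), or 0 when x = 0. The upper limit is the 97.5% point of Beta(x + 1, n − x).

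| Grouping | Placebo (95% CI) | Dose group (95% CI) | Dose minus placebo |
|---|---|---|---|
| As assigned | 1/10 = 10.0% (0.3 to 44.5) | 0/6 = 0% (0 to 45.9) | 0 − 10.0 = −10.0 points |
| As received, one-way error | 0/9 = 0% (0 to 33.6) | 1/7 = 14.3% (0.4 to 57.9) | 14.3 − 0 = +14.3 points |
| As received, two-way swap | 0/10 = 0% (0 to 30.8) | 1/6 = 16.7% (0.4 to 64.1) | 16.7 − 0 = +16.7 points |

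The direction of the observed difference reverses. The intervals overlap widely in every row, so this concerns where an event is displayed and has no bearing on statistical significance.

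**Denominators.** SAP 9.3 splits the AE tables by whether participants enrolled before or under Protocol v11.0, with separate denominators. If placebo participants fall in both parts, each AE table has fewer than 10 of them, and one participant is more than 10.0% of that column. The documents do not give the split. The ADA incidence table (SAP Table 36) is not split.

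**The case against.** The best defence is that SAP 3.3 was never meant as a rule for misdosing. Its sentence describes pooling across cohorts and sits beside the display order. SAP 6.3 defines all four populations by what was received, and the SAP preface says that the document expands on the protocol. A sensible statistician would follow the protocol. AEs are also listed by participant (Listings 13 and 14), deviations appear in Listing 3, and SAP 6.8 plans no formal tests, so no error rate or power is affected.

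Much of this stands. The wording is probably a slip, and a known case would remain traceable in the listings. But 6.3 settles who is in a population, not the column in which they are shown. The only SAP text that forms the placebo column uses assignment, and nothing elsewhere in the SAP restores the protocol's rule.

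A reader might infer two stronger claims, which the documents do not support.

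*That placebo PK samples are drawn but not assayed.* This would rest on Protocol 10.5.2: "Blood samples from all subjects who received a complete dose of SAR440894 (the PK population) will be analyzed for the concentration". The sentence does not say that only those samples are assayed, and SAP 10.1 lists concentrations for participants who did not complete dosing, who fall outside it. Protocol 7.2.2 and SAP 4.1 and 4.5.2 describe the assay without restriction by arm. The laboratory is blinded by masked barcodes (Protocol 10.3.2, SAP 4.4.6). SAP Table 7 has a placebo column for quantifiable concentrations. The PK sentence in SAP 3.3 governs reporting and is compatible with results existing. The documents leave the question open.

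*That a mix-up would go unseen.* The unblinded pharmacist keeps dispensing and accountability records (Protocol 4.5), monitors review them (Protocol 14), and wrong product is a named major deviation. An active-assigned participant given placebo should have no quantifiable concentration, and would then appear as a PK Population exclusion in SAP Table 8 and Listing 5.

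**Conclusion.** The point holds as a discrepancy of wording with a definite consequence. The SAP replaces the protocol's received-based placebo group with an assigned-based one, does not declare the change, and contradicts its own PK Population. Followed literally, it would put a documented wrong-product case in the wrong safety group.

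The size depends on an error that may never happen. With one such case and one event, placebo reads 1/10 instead of 0/9 and the dose group reads 0/6 instead of 1/7. With no dosing error the effect is nil. The illustration assumes full planned enrolment, a single misdosed participant given the cohort's own dose, and no split by protocol version. The conclusion about the rules themselves needs none of these assumptions.

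**What to change.** Three edits to the SAP:

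- **Section 3.3, pooling sentence:** define treatment group by the product and dose received, and form pooled placebo from participants who received placebo.
- **Section 6.3.1:** add that the Safety Population is grouped by treatment received, as in Protocol 10.5.1.
- **Section 3.3, PK sentence:** replace *assigned* with *received*, so that it agrees with 6.3.2 and the protocol.

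Make the edits before unblinding, since Protocol 10.5 requires the SAP to be prepared by then. The cost is a few words. No new data or tables are needed, and no planned number changes if everyone receives the assigned product (10 placebo, 6 per dose). Extra assays of placebo samples are not part of this fix, because the documents do not settle whether those samples are already assayed.
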